C.6 Baseline and Post-intervention. Prior to the testing, individuals will be asked to avoid alcohol consumption and moderate to vigorous physical activity 24 hours prior. Following the informed consent process, individuals will complete a brief menstrual history, 24-hour health status recall, and provide a saliva sample. Information about potential confounders and psychological symptoms also will be obtained using standardized methods supported by evidence of their validity (i.e., measures of symptoms of depression and anxiety, anxiety sensitivity, and physical activity history). These assessments will be repeated every 2 weeks and at the end of the six-week experiment. A body composition assessment via a dual-energy x-ray absorptiometry (DXA) will be completed. In a private room, the participants will fasten a wireless Zephyr™ BioHarness™ (Zephyr Technology, Auckland, New Zealand) below the sternum, (see figure 3). The Zephyr™ BioHarness™ will assess autonomic function via variability in heart rate. A baseline heart rate variability will involve adopting a seated position and measuring ECG while the participants rest for 5 minutes. Participants will complete the state portion of the State-Trait Anxiety Inventory (STAI), followed by a mental arithmetic task in which the participant will subtract by 13 from a 4-digit number for 10 minutes. Immediately after the mental arithmetic, participants will complete the state portion of the STAI. Participants will then complete a seated recovery for 5 minutes. Next, peak oxygen uptake (VO_{2Peak}) and peak power output (PPO) will be measured via a ramped bicycle protocol (Lode Excalibur Sport). Power output will be increased by 15 watts every minute until volitional exhaustion. Expired gases will be continuously measured via indirect calorimetry (Parvo Medics TrueOne 2400;

Parvo Medics, Salt Lake City, UT), and heart rate will be continuously monitored throughout the exercise test via a chest heart monitor (Polar; Polar Electro Inc., Lake Success, NY). The VO_{2peak} test will be administered so that participants can be prescribed the same exercise intensity, relative to their PPO, during exercise training. Saliva, DXA, vagal tone, peak oxygen uptake (VO_{2peak}), and sleep will be measured at baseline and after the six-week intervention.

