C. 7 High-Intensity Interval Training (HIIT). HIIT participants will complete three leg cycle ergometer bouts weekly. During the first two weeks, the participants will complete 13, 30-second high intensity exercise intervals at a wattage prescribed to elicit 67% of PPO. Each 30-second exercise interval will be followed by a 1-minute active recovery interval at 30% of PPO. Each week, prescribed wattage will be increased by 4% of PPO. Thus, in the final week, the training intensity will be at 87% of PPO (See table 1 for training example). At the start of the third week, the exercise duration will be increased. Specifically, the 13, 30-second-high intensity intervals will increase to 10, 60-second high intensity intervals. All sessions will start with a three-minute warm-up and end with a two-minute cool-down on the cycle ergometer. In sedentary panic disorder patients, a 12 day HIIT training intervention of similar initial exercise intensity was well tolerated and showed rapid reductions in symptoms (Plag, Ergec, Fydrich, & Strohle, 2019). During the exercise sessions, ratings of perceived exertion, quadriceps pain, and heart rate during the exercise sessions will be assessed 0, 5, 10, 15, 20 minutes into the HIIT.

C.7 Waitlist Control (WL). Participants randomly assigned to the waitlist will visit the laboratory in order to complete the baseline, bi-monthly assessments and post-assessments. They will be asked to maintain their current lifestyle. They will be given the option to receive a six-week supervised HIIT training program after the waitlist participation.

D. Primary Outcome Measures for the Specific Aim

D.1 Specific Aim 1. Evaluate the impact of six-weeks of high intensity interval training on sleep quality and whether the effect is accounted for by the change in vagal tone.

Pittsburgh Sleep Quality Index-(PSQI): The PSQI is the gold standard measure of self-reported sleep quality. It consists of 19 items. Scores range from 0-21, higher scores indicate poorer sleep quality. A global score ≥ 5 indicates poor sleep quality with a sensitivity of 0.90 and specificity of 0.87 compared to polysomnographically determined poor sleep (Buysse et al., 1989). The PSQI instructions will be modified to better assess rapid changes in usual sleep habits (last two weeks rather than the past month).

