Cardiac Vagal Tone: Each participant will place a bioharness monitor on in a private room. The R-R waveform will be sampled at 1000 hertz. Fast Fourier transformation will be applied, spectral power will be determined, and the average of the frequency domain will be calculated using Kubios analysis software (Tarvainen, Niskanen, Lipponen, Ranta-aho, & Karjalainen, 2014). After the frequency units from the heart cycles are converted to hertz, the vagal tone (high frequency band; 0.15-0.5 Hz), sympathetic tone (low frequency band; 0.05-0.15 Hz) and total power (0.017-0.5 Hz) will be calculated. The *apriori* focus is on changes in vagal tone.

Arithmetic Stress Task: Vagal tone will be measured at rest and during a stressor involving math calculations. Serial subtraction will be administered by a research team member dressed in white lab coat, with a clip board and pen for making notes. The team member will correct participants every time an incorrect answer is given and prompt participants to increase their pace every 15 seconds. Serial subtraction will involve sequentially subtracting 13 from a 4-digit number, and if an incorrect response is given, they will be asked to start over. The subtraction task will last a total of 10 minutes.

D.1.1 Expected Results. Based on our review of exercise training studies (McGranahan & O'Connor, 2021), we hypothesize HIIT to result in a clinically meaningful, moderate-sized or greater improvement in sleep quality. It is hypothesized that exercise-training induced changes in vagal tone will mediate the improvements in sleep quality. We do not expect improvements for sleep quality or vagal tone in the control group.

D.1.2 Statistical Power. A sample of 60 total participants will provide statistical power of 80%, at an alpha of 0.05. Assuming a moderate-sized interaction effect of 0.47 on sleep quality and a correlation of 0.85 between repeated measurements, the calculated sample size is 30 per group. Meta-analyses of participant drop out in exercise training trials shows that an average of 20% in the exercise groups and 15% in the control groups drop out (Kelley & Kelley, 2013). Using 20% attrition, recruiting 36 per group will result in 30 completers per group. The short-term (six-week) training duration should result in less than 20% compared to the meta-analysis which included primarily longer-term trials.

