D.1.3 Statistical Analysis. ANOVA will examine the effect of exercise training on sleep quality. Mediation of the effect by the change in vagal tone will be tested by adding the variable as a covariate to the model. A change in the significance of the f-value would indicate significant mediation (Baron & Kenny, 1986; Fiske, Kenny, & Taylor, 1982). To quantify the effect size exercise training has on sleep quality at weeks 2, 4, and 6 and vagal tone at baseline and post, Hedges' d will be calculated.

D. 2.0 Specific Aim 2. Evaluate the impact of six-weeks of high intensity interval training on sleep quality, statistically testing for the effect of the change in trait anxiety and hyperarousal symptoms.

State and Trait Anxiety Inventory: Trait anxiety will be used and is reduced after exercise training (J. W. Whitworth et al., 2019a).

The Posttraumatic Diagnostic Scale-5 (PDS-5): Hyperarousal symptoms will be measured using the hyperarousal subscale of the Posttraumatic Diagnostic Scale-5 (PDS-5). The full 24-item scale also will be used as part of the inclusion criteria to assess PTSD symptoms in the past month based on the diagnostic criteria for the DMS-5. The full PDS-5 assesses trauma history, symptom onset, and index of trauma. Internal consistency of the full PDS-5 and the hyperarousal subscale ≥ 0.90 .

D.2.1 Expected Results. Hyperarousal and anxiety symptoms are expected to decrease after HIIT and be correlated with improvements in sleep quality.

D.2.2 Statistical Analysis. A time-varying covariate analysis will determine if sleep quality changes are explained by the change in trait anxiety or hyperarousal at weeks 2-, 4-, or 6- of the intervention (Winer, 1991). To quantify the effect size exercise training has on PTSD symptoms and anxiety at weeks 2, 4, and 6, Hedges' d will be calculated.

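### The change in vagal tone is never measured before a follow-up sleep window, so Aim 1 can show that vagal tone changed along with sleep but not that it mediated the improvement

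*Combined protocol and SAP*

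**What the plan says.** - **Timing of vagal tone.** C.6 closes with "Saliva, DXA, vagal tone, peak oxygen uptake (VO_{2peak}), and sleep will be measured at baseline and after the six-week intervention". D.1.3 agrees on vagal tone, planning effect sizes for "sleep quality at weeks 2, 4, and 6 and vagal tone at baseline and post".
- **Two-weekly repeats.** C.6 also says "These assessments will be repeated every 2 weeks and at the end of the six-week experiment". That sentence follows the list of questionnaire measures and comes before the DXA and BioHarness text, so it does not cover the vagal recording.
- **Conditions within a visit.** D.1 adds that "Vagal tone will be measured at rest and during a stressor involving math calculations". This gives a second condition at the same visit, not another time point.
- **Sleep recall.** The PSQI instructions are changed to cover the "last two weeks rather than the past month".
- **Hypothesis.** D.1.1: "It is hypothesized that exercise-training induced changes in vagal tone will mediate the improvements in sleep quality".
- **Test.** D.1.3: "Mediation of the effect by the change in vagal tone will be tested by adding the variable as a covariate to the model". A shift in the significance of the F statistic is then read as mediation. No lagged model is described.
- **Timing of sleep.** The two sections differ. The closing sentence of C.6 lists sleep at baseline and post, while D.1.3 uses sleep at weeks 2, 4 and 6.

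**The concern.** A mediator should change before the outcome that it is meant to explain. Here the mediator is a change score that does not exist until the post visit, while the PSQI completed at that visit describes the two weeks leading up to it. Randomisation protects the effect of HIIT on vagal tone and the effect of HIIT on sleep. It does not protect the link between vagal tone and sleep, which could run either way or reflect a common cause.

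At stake is the mechanistic half of Aim 1. Applied as written, D.1.3 could label as mediation a pattern produced by better sleep raising vagal tone. The covariates of Aim 2 are planned for weeks 2, 4 and 6, so the protocol already uses intermediate measurement for its other candidate explanations.

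**Working it through.** **1. Timeline.** The recall period is from D.1, the sleep visits from D.1.3, and the vagal visits from C.6 and D.1.3.

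| PSQI at | Sleep period described | Only post-baseline vagal reading | Gap after the window ends |
|---|---|---|---|
| Week 2 | weeks 0–2 | about week 6 | 4 weeks |
| Week 4 | weeks 2–4 | about week 6 | 2 weeks |
| Week 6 | weeks 4–6 | about week 6 | 0 weeks |

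Follow-up sleep windows that start after a post-baseline vagal reading: 0 of 3. If sleep is measured only at baseline and post, as C.6 says, the count is 0 of 1. The result is the same under either reading. Baseline vagal tone does come earlier, but it precedes the intervention and cannot carry a treatment effect.

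**2. How often the D.1.3 rule would mislead.** The plan gives no figure for this, so I simulated trials in which sleep drives vagal tone and vagal tone has no effect on sleep.

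- Effect size: D.1.2 plans on "Assuming a moderate-sized interaction effect of 0.47 on sleep quality and a correlation of 0.85 between repeated measurements". If 0.47 is in SD units of a single PSQI score, the SD of a change is √(2(1 − 0.85)) = 0.548, and the effect on the change scale is 0.47 / 0.548 = 0.858. If 0.47 is already in change-score SD units, the effect is 0.47. D.1.2 does not say which.
- Sleep change: S = −δ·arm + e, with e of SD 1 and δ = 0.858 or 0.47.
- Vagal change: V = −r·S + √(1 − r²)·u, with u of SD 1. The within-arm correlation has size r = 0.3, 0.4 or 0.5. These values are assumptions, because the documents give none.
- 30 per arm (D.1.2).
- Rule: the arm effect has p < 0.05 in S ~ arm and p ≥ 0.05 in S ~ arm + V.

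| Among trials with a significant total effect | r = 0.3 | r = 0.4 | r = 0.5 |
|---|---|---|---|
| False mediation call, δ = 0.858 | 6% | 9% | 14% |
| False mediation call, δ = 0.47 | 16% | 25% | 33% |

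These are Monte Carlo figures and move by about a percentage point between runs. The total effect is significant in about 90.5% of trials at δ = 0.858 and 43.3% at δ = 0.47. As a share of all trials, the second row is therefore 0.16 × 0.433 = 7%, 0.25 × 0.433 = 11% and 0.33 × 0.433 = 14%.

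**3. Same-time reverse model.** Adjusted for arm, the S–V partial correlation is symmetric. The p-value for V in S ~ arm + V equals that for S in V ~ arm + S, and it was identical in every simulated trial. Fitting the model in reverse adds no information about direction.

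**4. A lagged model with added recordings.** I kept the same causal direction (sleep drives vagal tone) and assumed a correlation of 0.85 between all PSQI visits. The table shows how often week-4 vagal change is falsely significant for week-6 sleep.

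| Model for week-6 sleep | r = 0.3 | r = 0.4 | r = 0.5 |
|---|---|---|---|
| Change score, adjusted for arm | 20% | 32% | 49% |
| Adjusted for arm and baseline PSQI | 16% | 27% | 40% |
| Adjusted for arm, baseline and week-4 PSQI | about 5% | about 5% | about 5% |

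Without week-4 PSQI, persistence of sleep alone carries the false signal forward.

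**The case against.** The best defence is that a mediator measured at the same visit as the outcome is a common limitation, and that the D.1.3 rule misfires in only a minority of trials. The rule also responds to the true direction. With assumed values of effect 0.8, path 0.6 and residual SD 0.8, it fired in 94% of trials with a significant total effect when vagal tone fully drove sleep, against 26% when sleep drove vagal tone. That stands as a statement about frequencies under two clean models. It does not settle direction in one trial, where partial mediation and common causes are also possible.

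A reader might infer three stronger things that the documents do not support.

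- **That reverse causation would give a false mediation claim in 65%, 89% or 99% of trials.** Those are the rates at which the vagal coefficient itself is significant at r = 0.3, 0.4 and 0.5. D.1.3 judges mediation by the treatment effect losing significance, and that rule gives the much lower rates above.
- **That no lagged test of any kind is possible.** Only the hypothesised direction is closed. With sleep at weeks 2 and 4, as D.1.3 implies, earlier sleep change can be tested against week-6 vagal change.
- **That vagal tone is recorded at the end of each PSQI window.** There is no recording at weeks 2 or 4.

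It is also fair that extra recordings are not free. C.6 and C.3 ask for 24 hours without alcohol and exercise (moderate to vigorous in C.6, vigorous in C.3), and C.3 asks for 12 hours without caffeine. HIIT women train three times a week. The documents do not say that the interim assessments meet these conditions.

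**Conclusion.** The concern holds for the mediation claim of Aim 1. The timing finding rests on the documents alone and does not depend on how C.6 and D.1.3 are reconciled on sleep. The size does rest on assumptions. With 30 per arm and within-arm correlations of 0.3 to 0.5, reverse causation would be called mediation in about 6–14% of trials with a significant total effect, or 16–33% if 0.47 is in change-score SD units.

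The randomised comparison of sleep quality is untouched, as is the effect of HIIT on vagal tone. This is an inexpensive improvement that changes what the trial may conclude about mechanism. It is not a flaw in the main comparison.

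**What to change.** 1. **Limit the claim.** State in D.1.1 and D.1.3 that Aim 1 can conclude only that change in vagal tone accompanied change in sleep, not that it mediated it. The cost is wording and a weaker mechanistic statement.
2. **Reconcile the sleep schedule** in C.6 with D.1.3.
3. **Use the data already planned.** If the PSQI is collected at weeks 2 and 4, prespecify a test of whether sleep change at week 2 or 4 predicts week-6 vagal change, adjusted for arm. An association would make the reverse direction plausible. It would not prove it, because vagal tone at weeks 2 and 4 would be unknown. Do not rely on a same-time reverse model.
4. **Optional recordings.** Repeat the 5-minute seated recording at the week-2 and week-4 assessments under the same pre-visit restrictions. Test vagal change from baseline to week 4 against week-6 PSQI, adjusted for arm, baseline PSQI and week-4 PSQI. The last adjustment is essential. For 72 women this is 72 × 2 = 144 recordings with existing equipment, plus visit time and scheduling around training days. C.7 calls the waitlist interim visits bi-monthly, so confirm that these are the two-weekly assessments of C.6.

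Even with item 4, the lag gives time order only. It does not remove confounding between vagal tone and sleep, and the report should say so.

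### The power statement does not identify the test behind 30 per group; naming a baseline-adjusted week-6 PSQI contrast would make it checkable and, under gradual change, raise power from about 80–84% to about 92%

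*Combined protocol and SAP*

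**What the plan says.** D.1.2 (Statistical Power) states: "A sample of 60 total participants will provide statistical power of 80%, at an alpha of 0.05". The inputs are given as "Assuming a moderate-sized interaction effect of 0.47 on sleep quality and a correlation of 0.85 between repeated measurements", and from these "the calculated sample size is 30 per group". The section does not give the test, the number of measurement occasions, the units of 0.47, sidedness or any sphericity assumption.

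D.1.3 (Statistical Analysis) describes the primary analysis in one line: "ANOVA will examine the effect of exercise training on sleep quality".

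The documents point two ways on the number of sleep assessments:

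- **Two visits.** C.6 lists sleep with saliva, DXA, vagal tone and peak oxygen uptake, and says that "sleep will be measured at baseline and after the six-week intervention".
- **Four visits.** D.1.3 plans effect sizes for sleep quality at weeks 2, 4 and 6, and in the same sentence limits vagal tone to baseline and post. D.2.2 plans a time-varying covariate analysis of sleep change at those weeks. The PSQI description in D.1 shortens the recall period to two weeks to pick up rapid change.

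**The concern.** The natural reading of C.6 is a two-visit group-by-time comparison. For that test the stated inputs require clearly fewer than 30 per group, so the power line appears not to follow from its own assumptions. A four-visit ANOVA can give about 30, but only after choosing a time course that the plan does not state.

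Two things are at stake. The first is that D.1.2 is the only justification of the sample size, and a reader cannot tell which test it belongs to. With D.1.3 saying only that an ANOVA will be used, the primary test on sleep quality is not fixed before the data are seen. The second is that, if the intended test is the omnibus interaction over four visits, it spends three degrees of freedom on a question that Aim 1 poses as a single six-week effect.

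**Working it through.** **Inputs from D.1.2:** effect 0.47, r = 0.85, alpha 0.05, power 80%, 30 per group. **Assumptions, because the plan is silent:** two-sided test; 0.47 in SD units of the PSQI score (SD = 1); equal correlation between all visits.

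**1. Reproducing 30: four-visit group-by-time interaction (3 df).** Let δ be the between-group difference at each visit. Then λ = (n/2)·Σ(δ − mean δ)²/(1 − r), with 3 and 3(2n − 2) df. For a linear build-up, δ = 0.47 × (0, 1/3, 2/3, 1), the sum of squares is 0.1227 and at n = 30 λ = 15 × 0.1227/0.15 = 12.27.

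| Course of the difference | n per group for 80% | Power at 30 |
|---|---|---|
| Linear | 28 | 84.0% |
| Linear, epsilon 0.9 | 30 | 81.0% |
| 0, 0.5, 0.75, 1 of the effect | 28 | 83.4% |
| Both mid-visits at half the effect | 31 | 79.6% |
| Immediate and sustained | 21 | 93.7% |
| Only at week 6 | 21 | 93.7% |

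Gradual courses lie close to 30. The plan's figure can be reproduced, but only by supplying a time course and epsilon that it does not give.

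**2. Two-visit group-by-time test (change score).** SD of change = √(2(1 − 0.85)) = 0.548. Standardised effect = 0.47/0.548 = 0.858. Noncentral t gives 23 per group for 80% power (22 by the normal approximation) and 90.5% power at 30. To need 30 per group, r would have to be about 0.80 or the effect about 0.40.

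**3. Week-6 difference adjusted for baseline.** Residual SD = √(1 − 0.85²) = 0.527. Standardised effect = 0.47/0.527 = 0.892. This needs 21 per group and has 92.5% power at 30.

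**4. Sensitivity to r for the baseline-adjusted test at 30 per group.**

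- r = 0.80: SD √(1 − 0.64) = 0.600, effect 0.783, power about 85%.
- r = 0.70: SD √(1 − 0.49) = 0.714, effect 0.658, power about 71% (a change score has 64%).
- The 80% point: from step 2, 80% at 30 per group needs a standardised effect of 0.403/0.548 = 0.736. Then 1 − r² = (0.47/0.736)² = 0.408, so r is about 0.77. For a change score the corresponding r is about 0.80.

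**5. Sensitivity to the effect metric.** If 0.47 were in SD units of the change score, the two-visit test would need 73 per group and have 43.3% power at 30. That reading makes the stated r redundant, so raw-score units are the more natural reading, but D.1.2 does not say so.

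**6. After dropout.** The plan's 20% loss from 36 leaves 28.8. At 29 per group, power is 91.6% (baseline-adjusted), 89.5% (change score), 82.6% (omnibus, linear) and 78.0% (omnibus, mid-visits halfway).

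**The case against.** The strongest reply is that there is no arithmetic error. D.1.2 names no test, so a mismatch with the two-visit test contradicts nothing in the plan. The evidence for four visits is good: sleep effect sizes at weeks 2, 4 and 6, the time-varying analysis in D.2.2 and the two-week recall. Training intensity rises each week, so gradual change is a natural assumption, and it gives 28 per group, or 30 with a modest sphericity correction. An omnibus interaction is also legitimate where the time course is of interest. Finally, if the two-visit test was meant, 30 per group is more than enough.

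Most of this stands. A reader might infer from step 2 that 30 per group is a miscalculation, or from the table that only a near-worst-case time course lands near 30. The documents support neither: the powered test is not named, and several ordinary gradual courses give 28 to 31.

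Two points survive. Consistency with 30 under one set of unstated choices does not verify the figure, since the four-visit answer runs from 21 to 31 over the courses tabulated without a sphericity correction. And the omnibus test's lower power under gradual change follows from the plan's own inputs. That advantage does not hold for every course. If the effect is immediate and sustained, or appears only at week 6, the omnibus test has 93.7%, marginally above 92.5%.

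**Conclusion.** The point holds as an under-specified power statement with a better test available, and not as an error in the sample size. D.1.2 and D.1.3 do not identify the powered test, and C.6 conflicts with D.1.3 and D.2.2 on the sleep schedule. If the two-visit test is meant, 80% understates the power (90.5%). If the four-visit interaction is meant, 80% is about right under gradual change.

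Under gradual change, moving from the omnibus test to a baseline-adjusted week-6 contrast raises power at 30 per group from 79.6–84.0% to 92.5%. This rests on a two-sided test, 0.47 in PSQI SD units, r = 0.85 and equal correlations between visits. The value of r matters most, and D.1.2 gives neither a source nor a range for it. No participant's treatment and no enrolment figure is affected.

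**What to change.** 1. **D.1.3:** name the primary test as the between-group difference in PSQI at week 6, adjusted for baseline PSQI, two-sided at 0.05. Make weeks 2 and 4 secondary.
2. **D.1.2:** state that 0.47 is in SD units of the PSQI score, if that is what was meant, and give power for the named test at 30 per group: about 92% at r = 0.85, about 85% at r = 0.80 and about 71% at r = 0.70. Add the r at which power falls to 80% (about 0.77). If the sponsor prefers to keep the four-visit interaction, D.1.2 should instead state the number of visits, the assumed time course and the sphericity correction.
3. **C.6, D.1.3 and D.2.2:** reconcile when sleep is assessed.

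The cost is a few sentences and a recomputed power line. Baseline PSQI is already collected, and enrolment does not change. The one downside is that mid-visit differences lose primary status.

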Effects of a high-intensity interval training (HIIT) exercise intervention on sleep quality in
women exposed to trauma: A randomized controlled trial

Date: 9/16/2021

Methods

C.2 Research design. A randomized control trial design will be used. Participants will be randomly assigned to one of the two treatment arms in blocks of two to optimize statistical power and minimize potential bias (Spieth et al., 2016). Sequentially numbered sealed envelopes created by a third-party using research randomizer (www.randomizer.org) will be used to allocate participants to treatments.

C.3 Participants. Seventy-two women who meet the inclusion criteria will be invited to participate. The seven inclusion criteria are: (i) exposure to a traumatic event, (ii) persistent PTSD-related symptoms adequate to screen positive for PTSD (Posttraumatic Diagnostic Scale-5 total scores > 27), (iii) poor sleep quality (Pittsburgh Sleep Quality Index >5), (iv) failure to meet recommended level of physical activity for U.S. adults (<150-mins of moderate or 75-mins of vigorous physical activity [or a combination] per week), (v) able to safely perform high intensity exercise (no contraindications based on the Physical Activity Readiness Questionnaire), (vi) aged 18-39 years, (vii) a non-smoker, (viii) willing to avoid alcohol and vigorous physical activity 24 hours before visiting the lab, and (ix) willing to avoid caffeine for 12 hours before visiting the lab.

C.4 Recruitment.

Several recruitment approaches will be implemented to ensure the required sample size is obtained. These approaches included: (i) e-mails sent to selected campus listservs, (ii) recruitment announcements in college classrooms, (iii) flyers placed in the University Health Center and around town, (iv) public service announcement made over the radio, and (v) by word of mouth.

C.5 Online Screening. Individuals interested in volunteering will be screened for eligibility by completing online surveys presented using Qualtrics. Eligible individuals will be invited to visit the Exercise Psychology Laboratory.

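### The attrition allowance in D.1.2 is miscalculated: 36 per group at 20% attrition leaves 28.8 completers, not the 30 on which the 80% power rests

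*Combined protocol and SAP*

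**What the plan says.** Section D.1.2 (Statistical Power) sets the requirement: "A sample of 60 total participants will provide statistical power of 80%, at an alpha of 0.05". The stated inputs are an effect of 0.47 and "a correlation of 0.85 between repeated measurements", from which "the calculated sample size is 30 per group".

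The section then turns to dropout. It cites meta-analytic evidence from exercise trials that "an average of 20% in the exercise groups and 15% in the control groups drop out", and makes the allowance at the higher rate for both arms: "Using 20% attrition, recruiting 36 per group will result in 30 completers per group". A closing remark expects attrition below 20% because this trial is shorter than most of those in the meta-analysis, but gives no figure.

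Section C.3 carries the result forward as the recruitment total: "Seventy-two women who meet the inclusion criteria will be invited to participate". This is 2 × 36.

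**The concern.** Losing 20% of 36 does not leave 30. To end with a required number of completers, that number must be divided by the proportion retained. Multiplying it by one plus the dropout rate always gives too few, and 36 is exactly what that multiplication yields.

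The sentence is the only link between the 60 participants said to give 80% power and the 72 to be recruited. If it is wrong, a trial that meets its recruitment target and loses exactly the proportion it allowed for will still analyse fewer women than the plan says it needs. The stated power would then not apply to the sample the plan itself predicts.

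**Working it through.** **Inputs.** Required completers 30 per group (60 in total), power 80%, alpha 0.05, effect 0.47, correlation 0.85, attrition 20%, cited rates 20% (exercise) and 15% (control): all from D.1.2. Recruitment of 72, i.e. 36 per group: C.3 and D.1.2. The plan does not say whether alpha is one- or two-sided; two-sided is assumed below.

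**1. The plan's own figure.** 30 × (1 + 0.20) = 36. This reproduces the recruitment number. D.1.2 does not show the step, so the route is inferred from the result.

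**2. Completers from 36 recruited.** Completers = n × (1 − attrition).

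| Attrition (exercise / control) | Exercise | Control | Total |
|---|---|---|---|
| 20% / 20% (the allowance in D.1.2) | 36 × 0.80 = 28.8 | 28.8 | 57.6 |
| 20% / 15% (the cited rates) | 28.8 | 36 × 0.85 = 30.6 | 59.4 |
| 16.7% / 16.7% | 30 | 30 | 60 |

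The last row is the break-even: 1 − 30/36 = 0.167.

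**3. Recruitment that 30 completers would need at 20%.** 30 / (1 − 0.20) = 37.5, which rounds up to 38 per group (76 in total), against 36 (72).

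**4. Effect on power, taking the plan's 80% at 30 per group as true.** For a two-sided two-sample t test, the noncentrality is δ × √(n₁n₂ / (n₁ + n₂)) with n₁ + n₂ − 2 degrees of freedom. Solving for 80% at 30 per group gives δ = 0.7356. Holding δ there:

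| Completers per group | Power |
|---|---|
| 30 | 80.0% |
| 29 | 78.6% |
| 28.8 | 78.3% |
| 28 | 77.1% |
| 28.8 exercise, 30.6 control | 79.6% |

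**5. Effect on power from the stated 0.47 and 0.85.** D.1.2 does not say what metric 0.47 is in. If it is a standardised mean difference and the analysis is of baseline-to-post change, the standardised effect is 0.47 / √(2 × (1 − 0.85)) = 0.47 / 0.5477 = 0.858. Power is then 90.5% at 30 per group, 89.2% at 28.8 and 88.4% at 28, and 23 per group would be enough for 80%. Adjusting the post score for baseline needs 21 per group; comparing post scores alone needs 73. None of these three readings returns the plan's 30. That is a separate matter, but it means the figures in step 4 depend on accepting the plan's own statement.

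**The case against.** The strongest reply is that the slip has little practical effect. It costs 1.2 completers per group and, on the plan's own terms, 1.7 points of power (80.0% to 78.3%). D.1.2 presents 20% as a cautious figure and expects less; at 16.7% or below, 36 per group is enough. The control arm at its cited 15% exceeds 30. With both cited rates the total is 59.4, about half a participant short. Nor do the documents show that true power falls below 80%, since the change-score reading leaves it near 89%.

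All of this stands as a limit on the size of the problem. It does not make the sentence right. The sentence names 20% and applies it to both arms. The expectation of lower attrition carries no number, and the plan nowhere states or justifies 16.7%. With the arm-specific rates the exercise arm is still at 28.8. The change-score margin cannot be relied on while the plan names neither the effect-size metric nor the test behind its power figure.

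One further caution is fair. At 20% attrition in both arms, the chance that each arm separately reaches 30 of 36 is 0.401² = 16%, or 0.401 × 0.710 = 28% with 15% in control. These figures should not be given much weight: planning on expected numbers never guarantees a target, and even 38 per group would meet this criterion only 0.655² = 43% of the time.

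**Conclusion.** The concern holds. At the attrition D.1.2 states, 36 per group gives an expected 28.8 completers per group (57.6 in total), not 30 (60). This is plain arithmetic and depends on no assumption about the effect or the test.

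The consequence is small: power of 78.3% at 28.8 per group, or 77.1% at 28, provided that 30 per group gives exactly 80% under a two-sided t test. On the change-score reading power stays well above 80%. The finding is a wrong figure underlying the recruitment total and the power statement, and it should be corrected. It does not show that the trial is too small.

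**What to change.** In D.1.2, replace the sentence on attrition with one to this effect: *With 20% attrition, 36 per group gives about 29 completers per group (28.8; 57.6 in total); 30 per group is reached only if attrition is 16.7% or less.*

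Then restate the power at 28 to 29 completers per group and name the test and effect-size metric it refers to. If the plan's 80% at 30 per group is kept as the reference, the restated figure is about 77% to 79%. If attrition below 20% is to be relied on, give the expected rate and the reason for it.

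The 72 in C.3 can stay. Recruitment of 38 per group would follow only if the team wished to keep both 30 completers and 20% attrition; the size of the shortfall does not call for it.

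The cost is a sentence or two and possibly a slightly less favourable stated power. Enrolment, design and analysis do not change.
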